Note: the number of new or enlarging T2 (with and without T1 Gd+) will be provided by central reading for each of the Periods including the Sequential Visit Periods, except for Period 3.1. For Period 3.1, the sum of the Sequential Visit Periods 100.1, 100.2 and 100.3 will be calculated.

For the calculation of the CUA lesion count, only T2 lesions that did not emerge from a T1 Gd+ lesion will be taken into account.

- Total active T2 lesion count (without T1 Gd+) =
Total new T2 lesion count without T1 Gd+
+ Total enlarging T2 lesion count without T1 Gd+

and will be standardized to the length of the Period (i.e. annualized). Total active T2 lesion count (without T1 Gd+) will only be calculated if T1 Gd+ counts for beginning and end of the corresponding Period are non-missing.

CUA lesion count

The number of CUA lesions for a Period will be defined as the sum of the T1 Gd+ and new or enlarging T2 counts for the respective Period and will be standardized to one scan (for T1) or one year (for T2) to harmonize the units of the 2 assessments.

$\#CUA(p_{\text{post-Baseline}})$ = Annualized CUA lesion count (by post-Baseline Period per 1 year)
= Mean T1 Gd+ lesion count (by Period i)
+ Annualized total active T2 lesion count (without T1 Gd+)
(by Period i per 1 year) Different from the primary analysis, T2

lesion count will be standardized to 1 year instead of 1 month due to longer periods and for comparison with other studies,

The CUA lesion count will only be calculated if both components (T1 and T2) are non-missing.

Data Handling in case of major PDs

PDs will not be considered in the planned statistical analyses (i.e., all data will be analyzed independent from any reported PD) except for PD due to MRI taken during steroid treatment (MRI will be excluded from the primary analysis).

Covariates and stratification factors

Age

Age (years) at time of Informed Consent (loaded from iRT). Missing age will be replaced as follows if used as a covariate:

- Age will be estimated from the year of birth (year of IC – year of birth), as recorded in the electronic Case Report Form (eCRF),
- If year of birth is missing, age will be imputed by the mean age of the FAS.

EDSS at Baseline

Expanded Disability Status Scale (EDSS) at Baseline will be categorized by:

- ≤ 3 (reference),
- >3 .

Missing EDSS at Baseline will be imputed by the median Baseline EDSS of the FAS if used as a stratification factor.

Pooled centers

Some centers will have few eligible subjects only. Therefore, the centers will be pooled together by country except for

- sites that have more than 12 subjects in the FAS (i.e. these sites will not be pooled with any other site).
- for countries that have 6 subjects or less in the FAS that will be pooled as follows:
- Scandinavia = Finland and Sweden
- Mediterranean = Italy and Spain
- Austria-Hungary = Austria and Hungary

MRI specific covariates

Time between scans: in Months

Time between scans (in Months) is calculated as follows:

- Time between scans (in Months) = (MRI date of the Visit - MRI of the previous Visit + 1) / 30.4375. i.e.:
 - If (Visit=Month 1) then Time between scans (in Months) = (MRI date at Month 1 - MRI date at Baseline + 1) / 30.4375
 - If (Visit=Month 2) then Time between scans (in Months) = (MRI date at Month 2 - MRI date at Month 1 + 1) / 30.4375
 - If (Visit=Month 3) then Time between scans (in Months) = (MRI date at Month 3 - MRI date at Month 2 + 1) / 30.4375
 - If (Visit=Month 6) then Time between scans (in Months) = (MRI date at Month 6 - MRI date at Month 3 + 1) / 30.4375

If the corresponding MRI is available and the time between scans is missing (due to preceding MRI being missing) it will be replaced by expected time as follows:

- Month 1/2/3 Visit =1
- Month 6 Visit =3.

Time between scans: in Years

Time between scans (in Years) is calculated as follows:

- Time between scans (in Years) = (MRI date of the Visit - MRI of the previous Visit + 1) / 365.25, i.e.:
 - If (Visit= Month 1) then Time between scans (in Years) = (MRI date at Month 1 - MRI date at Baseline + 1) / 365.25
 - If (Visit= Month 2) then Time between scans (in Years) = (MRI date at Month 2 - MRI date at Month 1 + 1) / 365.25
 - If (Visit= Month 3) then Time between scans (in Years) = (MRI date at Month 3 - MRI date at Month 2 + 1) / 365.25
 - If (Visit= Month 6) then Time between scans (in Years) = (MRI date at Month 6 - MRI date at Month 3 + 1) / 365.25
 - If (Visit= Month 12) then Time between scans (in Years) = (MRI date at Month 12 - MRI date at Month 6 + 1) / 365.25
 - If (Visit= Month 15) then Time between scans (in Years) = (MRI date at Month 15 - MRI date at Month 12 + 1) / 365.25
 - If (Visit= Month 18) then Time between scans (in Years) = (MRI date at Month 18 - MRI date at Month 15 + 1) / 365.25
 - If (Visit= Month 24) then Time between scans (in Years) = (MRI date at Month 24 - MRI date at Month 18 + 1) / 365.25

If the corresponding MRI is available and the time between scans is missing (due to preceding MRI being missing) it will be replaced by expected time as follows:

- Month 1/2/3 Visit =1
- Month 6 Visit =3
- Month 12 Visit =6
- Month 15 Visit =3
- Month 18 Visit =3
- Month 24 Visit =6.

Software(s)

All analyses will be performed using SAS® Software version 9.3, or higher.

10 Trial Participants

The subsections in this section include specifications for reporting subject disposition and treatment/study discontinuation. Additionally, procedures for reporting protocol deviations are provided.

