8.4 Analysis Sets

The following analysis sets are defined:

- Enrolled Set: all subjects who provided informed consent
- ITT (intent-to-treat) Set: all subjects classified as eligible
- FAS (Full Analysis Set): all subjects from the ITT who received at least one dose of the trial treatment
- Treatment Completer Set – Year 1: All subjects from the FAS who completed the full treatment course of the first year.
- Treatment Completer Set – Year 2: All subjects from the FAS who completed the full treatment course of the first and the second year.
- Safety set: all subjects who have received at least one dose of the trial treatment.

The primary analysis and all efficacy analyses will be performed on the FAS. As a robustness analysis the primary analysis will be repeated on the ITT (if different from the FAS) and the Treatment Completer Sets. All safety analyses will be performed on the Safety set.

Subjects who have withdrawn consent for the trial will be included in the analysis unless it was specified by them that their data not be used, after clarification of the level of withdrawal by the Investigator.

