8.2 Definition of Analysis Sets and Subgroups

Enrolled Set (ES)

All subjects enrolled in the study, i.e., all subjects with a signed informed consent.

Intent-to-treat Set (ITT)

All subjects classified as eligible (i.e., medication assigned by iRT at the Baseline Visit).

Full Analysis Set (FAS)

All subjects in the ITT treated with at least one dose of study medication.

Treatment Completer Set – Year 1 (TCS-1)

All subjects from the FAS who completed the full Treatment Course of the first year (Treatment Course 1). Subjects will be classified as Treatment Completer for the first year if they have a compliance greater than or equal to 100% for Treatment Course 1.

Treatment Completer Set – Year 2 (TCS-2)

All subjects from the FAS who completed the full Treatment Course of the first and the second year. Subjects will be classified as Treatment Completer for the second year if they have a compliance greater than or equal to 100% for Treatment Course 1 and Treatment Course 2 and received the treatment without delay (see Section 9 for definition).

Safety Analysis Set (SAF)

All subjects treated with at least one dose of study medication.

Unless otherwise specified, all efficacy analyses will be performed on the FAS.

Some tertiary analyses will be repeated on the Treatment Completer Sets and the primary analysis, on the ITT (if different from FAS), to evaluate the robustness of the primary results to deviations of the planned treatment regimen. Further details are given in the respective sections. All safety analyses will be performed on the SAF.

Additional Subgroup or Subset Analysis Sets

Subgroup analyses will be performed on subgroups as defined below.

- High-relapse activity (HRA)
 - HRA: at least 2 relapses in the previous year (i.e. the number of historical relapses within 12 months prior to Baseline ≥ 2) regardless of prior use of DMDs
 - Non-HRA: otherwise

Unless otherwise indicated, all descriptive statistical analyses will be presented separately for the HRA subgroups.

- Previous treatment with Disease Modifying Drugs (DMDs):
 - DMD pre-treated: Subjects will be categorized as DMD pre-treated if they have taken DMDs any time before start of study medication. Details of the definition of DMDs are specified in Appendix 1 (Section 18.1).
 - Pre-treatment naïve: all subjects not classified as DMD pre-treated.

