Compliance for each year (course) and total will be calculated for all subjects that started the respective treatment period (i.e. taken at least one tablet) as an average of available records obtained for the corresponding treatment weeks. That means, treatment weeks after the subject’s treatment discontinuation are not included in the derivation, records of 0 compliance for the corresponding treatment weeks are included in the derivation as such, and missing records result in missing compliance for the respective treatment period.

In addition, compliance will be categorized as follows:

- < 60%
- [60%-80%[
- [80%-90%[
- [90%-110%]
- >110%

The number of planned tablets is based on the weight at the beginning of each treatment course (Table 2).

Table 2: Dose of Mavenclad® per treatment week by subject weight in each treatment year

Weight range	Dose in mg (number tablets) per treatment week	
	Treatment week 1	Treatment week 5
40 to <50	40 mg (4 tablets)	40 mg (4 tablets)
50 to <60	50 mg (5 tablets)	50 mg (5 tablets)
60 to <70	60 mg (6 tablets)	60 mg (6 tablets)
70 to <80	70 mg (7 tablets)	70 mg (7 tablets)
80 to <90	80 mg (8 tablets)	70 mg (7 tablets)
90 to <100	90 mg (9 tablets)	80 mg (8 tablets)
100 to <110	100 mg (10 tablets)	90 mg (9 tablets)
110 and above	100 mg (10 tablets)	100 mg (10 tablets)

The number of subjects with the same planned dosing schema in both Treatments Courses and a different planned dosing schema (i.e. subjects exchanged weight range as defined in the table above) in Treatment Course 2 will be presented for all subjects, who have started Treatment Course 2 (i.e. taken at least one tablet in Treatment Course 2).

The time difference between the start of the Treatment Course 1 Treatment Period and the start of the Treatment Course 2 Treatment Period will be calculated as follows:

- Relative Start of Treatment Course 2 (days) = Start of Treatment Course 2 - Start of Treatment Course 1 + 1.

The Relative Start of Treatment Course 2 will be presented together with the number of subjects in the following groups for the SAF:

- Treatment Course 2 not started,
 - and discontinued before the Month 12 Visit,
 - and discontinued at or after Month 12 Visit
 - Lymphocyte count < 800 cells/mm³ at Month 12 Visit,
 - Reason potentially related to COVID-19
- Treatment Course 2 started,
 - and not delayed (see Section 9 for definition),
 - and delayed,

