Primary (FAS)	
 1. Period 3 (Month 3-6): $\Delta\text{CUA}(p_3)$ (Hypothesis 3) 2. Period 2 (Month 2-6): $\Delta\text{CUA}(p_2)$ (Hypothesis 2) 3. Period 1 (Month 1-6): $\Delta\text{CUA}(p_1)$ (Hypothesis 1) 	
P-values for the three Hypotheses from the Wilcoxon signed-rank test will be presented. The testing procedure will stop as soon as one of the hypotheses cannot be rejected following the pre-specified order (H3, H2, H1). Due to this sequential order of tests an adjustment for a potential type-I-error inflation due to the multiple testing is not required.
 
The Wilcoxon signed-rank test will be complemented by the estimated Least Square Means (LS Means) and corresponding Standard Errors (SE) including one-sided p-values as well as two-sided p-value and 95% CIs from the mixed-effects linear model with the following adjusting factors:
 
 • Baseline score, • Age (in years), • EDSS at Baseline (≤ 3, >3), • Within-pooled center correlation. 
In addition, the distribution of $\text{CUA}(p_i)$ and $\Delta\text{CUA}(p_i)$ will be displayed graphically using box plots.
	
Missing observations: Subjects with a missing CUA lesion count at either the Baseline Period or the respective post-Baseline Period will not be included in the analysis.

$\Delta\text{CUA}(p_i)$ = Difference in the standardized CUA lesion count between Period i and the Baseline Period (a) 6-month interim analysis
			

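### The SAP drops the primary-endpoint repeat on treatment completers that the protocol requires, does not declare it, and keeps only an ITT repeat that does not address incomplete Course 1 dosing

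*SAP*

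**What the plan says.** Protocol 8.4 names the FAS as the primary population and adds: "As a robustness analysis the primary analysis will be repeated on the ITT (if different from the FAS) and the Treatment Completer Sets". The condition in brackets applies to the ITT set only. The completer repeat is unconditional.

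SAP 8.2 divides the work differently: "Some tertiary analyses will be repeated on the Treatment Completer Sets and the primary analysis, on the ITT (if different from FAS". It gives the purpose of these repeats as "to evaluate the robustness of the primary results to deviations of the planned treatment regimen" and refers to later sections for details.

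The sets are defined in SAP 8.2:
- ITT: "All subjects classified as eligible (i.e., medication assigned by iRT at the Baseline Visit".
- FAS: "All subjects in the ITT treated with at least one dose of study medication".
- TCS-1: FAS subjects who completed Course 1, operationalized as "compliance greater than or equal to 100% for Treatment Course 1".
- TCS-2: the same for both courses, with Course 2 not delayed.

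For the primary analysis, SAP 14.1.1 states: "Subjects with a missing CUA lesion count at either the Baseline Period or the respective post-Baseline Period will not be included in the analysis". SAP Section 13 derives course compliance as the average over treatment weeks, where weeks after "treatment discontinuation are not included in the derivation".

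**The concern.** The primary objective is onset of action after Course 1, which consists of two treatment weeks. The second is dispensed at the Month 1 visit (Protocol 7.1.4), and the three tested periods start at the Month 1, 2 and 3 scans. A subject who misses the second week therefore contributes to all three periods with about half the planned tablets. Such subjects stay in the FAS, and under SAP Section 9 all data are analyzed whatever the protocol deviation, except MRIs taken during steroid treatment.

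The completer repeat is the analysis that would show whether these subjects move the Month 1-6 result. The SAP removes it for the primary endpoints without saying so, and leaves a repeat on a set that still contains every partly dosed subject. A reader of the report could take the ITT repeat as evidence of robustness to regimen deviations, which it is not.

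**Working it through.** No stated sample size, power or alpha is at issue, so there is no plan figure to reproduce. The check sets the sections side by side and then applies the SAP's own rules.

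**1. Where each repeat is planned**

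| Source | ITT repeat of primary | Completer repeat of primary |
|---|---|---|
| Protocol 8.4 | yes, if different from FAS | yes |
| SAP 8.2 | yes, if different from FAS | no; some tertiary analyses only |
| SAP 14.1.1 and 14.1.2 tables | no row | no row |
| SAP Section 7 (changes from protocol) | – | not mentioned |

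Every row in 14.1.1 and 14.1.2 is the FAS, or a subgroup or subset of it. TCS-1 and TCS-2 rows appear in 14.3.1, for the yearly change in annualized CUA count.

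**2. What the ITT repeat can show**

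ITT minus FAS is the set of subjects assigned medication but never dosed. Most would have no post-Baseline CUA count and would be dropped under the 14.1.1 rule. If k of them do have evaluable scans, take the planned 265 subjects as the FAS and assume a mean change of 0 in the k undosed subjects. Then

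ITT mean = FAS mean × 265 / (265 + k).

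| k | 0 | 1 | 3 | 5 | 10 |
|---|---|---|---|---|---|
| ratio | 1.000 | 0.996 | 0.989 | 0.981 | 0.964 |

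Whatever k is, the repeat adds undosed subjects and removes no partly dosed one.

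**3. What the 14.3.1 completer repeat can show**

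| | Primary | Yearly tertiary repeat |
|---|---|---|
| Period | Month 1, 2 or 3 to Month 6 | Baseline to Month 12; Month 12 to 24 |
| T2 component | per month | per year |
| Central reading | primary process | separate tertiary process (SAP Section 9) |
| Test | Wilcoxon signed-rank, plus linear model | linear model only |
| Timing | Month 6 analysis | final analysis |

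Period 12.1 contains Months 1-6, so it bears on the question, but only indirectly.

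**4. Whether TCS-1 as derived excludes partly dosed subjects**

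Inputs are the tablets per treatment week in SAP Table 2. For a subject who takes all of week 1 and then discontinues, week 2 is left out, so course compliance = 100 × w1 / w1 = 100%. The share of the course actually taken is w1 / (w1 + w2):
- 40 to <80 kg and 110 kg or more (equal weeks): 50.0%
- 80 to <90 kg: 8/15 = 53.3%
- 90 to <100 kg: 9/17 = 52.9%
- 100 to <110 kg: 10/19 = 52.6%

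A subject who takes the same tablets but is not recorded as discontinued scores (100 + 0)/2 = 50% and is excluded. Two subjects with identical exposure are thus classified differently.

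**5. Size**

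The share d with incomplete Course 1 is not given. Assumed values of 1%, 2%, 5% and 10% of 265 leave about 262, 260, 252 and 238 subjects in TCS-1. If partly dosed subjects had a fraction f of the full mean change, the FAS mean would be 1 − d(1 − f) times the completer mean. For d of 3% to 10%, that is 1.5% to 5% smaller at f = 0.5, 3% to 10% smaller at f = 0, and unchanged at f = 1. Both d and f are assumptions, so these figures show scale only.

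**The case against.** The strongest case on the other side has five parts.

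- **The SAP keeps a completer check.** The yearly CUA change is repeated on TCS-1 and TCS-2, SAP 8.2 presents such repeats as serving the primary results, and compliance is tabulated at the interim analysis. This stands in part. A reader might infer that the primary result has no check at all against incomplete dosing, and the documents do not support that. What is missing is a direct check on Periods 1 to 3.
- **The ITT repeat is not empty by construction.** A reader might infer that it cannot differ from the FAS result. That is not established. Protocol 5.5.2 keeps subjects withdrawn from trial medication in scheduled assessments, nothing bars an assigned but undosed subject from having scans, and both documents make the repeat conditional on a difference. It is usually identical, and in any case it answers a different question.
- **The sentence in 8.2 may be a drafting slip.** The stated purpose fits the completer sets better than the ITT. Even so, 14.1.2 has no completer row under any reading.
- **The bias would be conservative.** If partly dosed subjects benefit less, the FAS understates the effect and a positive result is not threatened. This is plausible but rests on an assumption that the repeat would examine.
- **A row added now is late.** SAP 6.2 and Section 7 treat the primary analysis as already performed. This is correct and affects labeling, not whether a protocol commitment should be met or its omission explained.

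**Conclusion.** The protocol and SAP disagree on a robustness analysis of the primary endpoints, and the SAP's list of changes is silent on it. The retained ITT repeat does not serve the purpose SAP 8.2 assigns to these repeats. Completer evidence comes only from a tertiary analysis on a different period, scale and central reading, without the Wilcoxon test.

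The effect on the primary result is unknown. The scale figures above depend wholly on assumed shares and assumed partial effects, and do not support a claim that the primary conclusion is at risk. Nor do the documents show whether a completer repeat was run at Month 6 outside this SAP. The point is modest: an undeclared departure that is cheap to repair.

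Two qualifications matter for the repair. TCS-2 needs Course 2 data and cannot be determined for a Month 6 analysis, so TCS-1 is the relevant set. And TCS-1, by its present compliance criterion, admits subjects who stop after treatment week 1, so rerunning it unchanged would leave in a group it is meant to remove.

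**What to change.** - Add a row 'Sensitivity (TCS-1)' to SAP 14.1.2 for Periods 3, 2 and 1, with the method and missing-data rule of 14.1.1.
- Correct the sentence in SAP 8.2 so that the completer repeat covers the primary analysis. Keep the conditional ITT repeat, which Protocol 8.4 requires.
- State in SAP Section 7 that TCS-2 does not apply at Month 6, and that the TCS-1 repeat was specified in the protocol but run after the primary analysis. Label it that way in the report.
- Derive TCS-1 from all planned Course 1 tablets, counting a treatment week not taken after discontinuation as zero. The compliance rule then agrees with the set's description as completion of the full course.

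Cost: one rerun of existing code, a small change to one derivation, and slightly fewer subjects in that row. The new TCS-1 derivation would also carry through to the 14.3.1 repeats.
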